## **Methods**

This study will be a 1 year randomized controlled trial to assess the impact of the “Lung Attack Alert” on rates of follow up by PCP of their patients following presentation to the ED for an AECOPD. The tool being assessed is labeled as the “Lung Attack Alert”(see **Appendix 1**). This is a novel information sheet that is intended for the PCP. The Lung Attack Alert summarizes the following points:

- a) that the PCP’s COPD patient has had a presentation to the ED for an AECOPD but did not require a prolonged hospital admission;
- b) a description of the discharge management from the ED will be provided;
- c) a recommendation to the PCP to follow up with the patient within 1-2 weeks after discharge from the ED;
- d) Care gaps identified in the patients chronic management of COPD based on the Canadian Thoracic Society 2007(updated 2008) guidelines will be highlighted for the PCP to address at the next outpatient follow up

Each Lung Attack Alert will be **individualized** to the patients care gap(s) identified during screening.

This study will enroll consecutive patients who present to the ED at the University of Alberta Hospital and the North East Community Center (both located in urban Edmonton), who present with an AECOPD, but who do not require admission to hospital.

ED physicians or the study coordinator will screen patients who present to the ED with an AECOPD, who have recovered from the acute event and are considered safe for discharge. All patients will receive usual care within the ED prior to screening and entry into the study. This may consist of the use of any or all of the following: oxygen, acute bronchodilators (+/- use of nebulizers or MDI), administration of oral/IV corticosteroids, intravenous fluids, non-invasive ventilation (NIV), oral or intravenous antibiotics as required.

Patients will be screened by either the ED physicians who will notify our study coordinator regarding the eligibility of a patient or directly by the study coordinator. Eligible patients (**Appendix 2**) will be provided with a patient information sheet (**Appendix 3**) outlining the rationale for the study. If the patient is agreeable to participate, a consent form will be signed and witnessed by either the ED physician or study coordinator (**Appendix 4**). To be enrolled into the study patients must satisfy all inclusion and exclusion criteria.

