After normal working hours(see below), when research staff are not available, patients who are eligible and who have consented to enter the study but have been discharged from the ED, will be contacted by the study coordinator the next morning by phone. Randomization will take place at that time and the appropriate process will take place thereafter. Those patients who are discharged from the ED will receive the outpatient treatment package (by the consenting ED physician) used in the study (Appendix 5) for the medical management of their AECOPD. The outpatient medication package will be readily available in the ED, in a reserved area for the study. This is to ensure that there is no delay in their treatment, as well, that their acute management does not impact the effect of the Lung Attack Alert.

As per the above randomization process, patients will be randomized into either the **control** group or the **intervention** group using a web-based randomization process (Epidemiology Coordinating and Research {EPICORE} Centre, Edmonton, AB; <http://www.epicore.ualberta.ca>).

The **control** group will be discharged from the ED, with the standardized outpatient protocol (Appendix 5) and will be advised to follow up with their PCP. They will be provided with general information regarding COPD in the form of the "Breathworks" program pamphlets established by the Canadian Lung Association. These are readily available in print and online, and they are information guides for patients with COPD. The patients will then be contacted by a research staff member unaware of the allocation of treatment at day 30 and 90 post discharge from the ED to discuss the primary and secondary outcomes (**Appendix 7**).

The **intervention** group will also be advised to follow up with their PCP, along with the standardized outpatient protocol for their acute exacerbation (Appendix

5). They will be provided with general information regarding COPD in the form of the “Breathworks” program. The intervention group will have the Lung Attack Alert form completed by the research study staff. The form will highlight the information already discussed earlier. This will then be faxed to their primary care physician by the study coordinator. The patients will then be contacted by a research staff member unaware of the allocation of treatment at day 30 and 90 post discharge from the ED to discuss the primary and secondary outcomes (**Appendix 7**).

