## **Outcomes**

The **Primary Endpoint** of this study is the rate of follow up of the patient by their primary care provider for review of the acute and chronic management of their COPD and addressing any issues on the Lung Attack Alert, within the first 90 days after discharge from the ED. The study coordinator will contact all patients enrolled on day 30 after admission to the ED to determine if a follow up visit has occurred and if any of the recommendations noted on the Lung Attack Alert have been implemented.

A number of **Secondary Endpoints** will be collected. These include 1) relapse of the AECOPD requiring acute intervention (ED or clinic) within the 90-day study period; 2) admission to the hospital within the 90-day study period; 3) review and adjustment of the management of COPD at day 90 post discharge from the ED 4) Proportion of patients who completed their acute management within the 90-day study period and 5) length of stay within the ED.

The study coordinator will contact the PCP of patients in the intervention group to survey the usefulness of the Lung Attack Alert once the study is complete. This survey will assess the clinical utility of the alert and the ease of use of the information provided in the alert to aid in clinical management.

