## **Statistics**

### **Sample Size Considerations:**

Calculations for the estimated sample size were completed using a formula for calculation of dichotomous response variables with two independent samples. We assumed  $\alpha = 0.05$  (accepted standard value), power  $(1 - \beta) = 0.80$ , and that 30% of patients in the control group would see their PCP within 30-days. This estimate of 30-day follow-up is taken directly from recent administrative data from Alberta. The sample size was therefore calculated to detect a 30% absolute difference in 30-day follow-up (30% of the standard-care vs. 60% of enhanced care groups). In addition, we used 1-tailed estimates due to the assumption that the intervention will not **decrease** the follow-up of patients with COPD. The total sample size was estimated at 98 (49/group) patients; however, if we assume ~10% attrition (see previous COPD study), the total sample size is estimated at 110 patients.

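### The protocol names two different day-30 callers: a staff member blind to allocation, and the study coordinator, who faxes the intervention-only alert

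*Combined protocol and SAP*

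**What the plan says.** The Methods text describing the control and intervention groups (it follows the Exclusion list) uses the same arrangement for each arm. Patients are "contacted by a research staff member unaware of the allocation of treatment at day 30 and 90 post discharge from the ED", and the purpose of the contact is to cover the primary and secondary outcomes, with Appendix 7 cited.

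The Outcomes section assigns the day-30 contact to someone else: "The study coordinator will contact all patients enrolled on day 30 after admission to the ED". That contact establishes whether a follow-up visit took place and "if any of the recommendations noted on the Lung Attack Alert have been implemented". Outcomes names no caller for day 90.

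On who handles the alert, the same Methods text says "The intervention group will have the Lung Attack Alert form completed by the research study staff", and then "This will then be faxed to their primary care physician by the study coordinator". For patients discharged after hours, the coordinator also makes the next-morning phone call at which randomisation takes place.

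**The concern.** As written, site staff have two instructions for one call. One keeps the caller blind. The other gives the call to a person who knows which patients had an alert sent.

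The call matters because it collects the visit outcome. The sample size section assumes that "30% of patients in the control group would see their PCP within 30-days", and the principal analysis section also takes 30-day visits as primary. Outcomes sets the primary endpoint at 90 days; that is a separate conflict, not resolved here. Outcomes also defines the endpoint as more than attendance. The follow-up must be "for review of the acute and chronic management of their COPD and addressing any issues on the Lung Attack Alert", which leaves room for judgement when a patient describes a visit by phone.

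The supplied text describes record checks and two-physician adjudication for relapse, but neither for the primary care visit. Blinding of the caller is the only safeguard it states for this outcome. In addition, asking about alert recommendations is a question that has no counterpart in the control arm.

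**Working it through.** The plan gives no figure on this point, so the main check is a comparison of text.

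| Item | Methods, group descriptions | Outcomes |
|---|---|---|
| Day-30 caller | Staff member unaware of allocation, both arms | Study coordinator, all patients |
| Day-90 caller | Staff member unaware of allocation, both arms | Not named |
| Day 30 counted from | ED discharge | ED admission |
| Who faxes the alert (intervention only) | Study coordinator | – |
| Who completes the alert form | Research study staff | – |

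The two statements could both be true only if a second, blinded coordinator made the calls. The supplied text does not provide for one. The conflict is confined to day 30.

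**How many miscounted patients would matter.** Inputs: 49 per arm and a 30% control rate, both from the sample size section. 0.30 × 49 = 14.7, taken as 15. For a control visits and b intervention visits, the uncorrected Pearson statistic is

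χ² = 98 × [a(49 − b) − b(49 − a)]² / [49 × 49 × (a + b)(98 − a − b)].

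- 15 v 20: 98 × 245² / (2401 × 35 × 63) = 1.11, p = 0.292
- 15 v 24: 98 × 441² / (2401 × 39 × 59) = 3.45, p = 0.063
- 15 v 25: 98 × 490² / (2401 × 40 × 58) = 4.22, p = 0.040

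The two-sided threshold is therefore 25. From no difference that takes 25 − 15 = 10 miscounted patients, or 10/34 = 29% of the intervention patients without a visit. From 20 it takes 25 − 20 = 5, or 5/29 = 17%.

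With continuity correction, 49 is subtracted from the absolute difference before squaring. 15 v 25 then gives p = 0.064 and 15 v 26 gives p = 0.041, so the counts become 11 and 6.

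The sample size section plans on a one-tailed basis. One-sided and uncorrected, the threshold falls to 23, so the counts are 23 − 15 = 8 and 23 − 20 = 3.

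**Effect on the false-positive rate, with assumed bias sizes.** The true rate is 30% in both arms, with 49 per arm.

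| Recorded intervention rate | Two-sided rejection (exact binomial enumeration, uncorrected test) |
|---|---|
| 30% | 4.9% |
| 35% | 8.0% |
| 40% | 17.4% |
| 45% | 33.2% |

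The last row requires 15/70 = 21% of true non-visits to be recorded as visits. A milder assumption is that 5% to 10% of non-visits are misrecorded. The recorded rate is then 0.30 + 0.70 × 0.05 = 33.5% to 0.30 + 0.70 × 0.10 = 37%. By normal approximation, rejection is about 7% to 11% two-sided, or 10% to 18% one-sided.

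**The case against.** The strongest reply is that blinded assessment is already planned. Methods states it for each arm, for both days and for all outcomes, and one sentence in Outcomes may simply use the coordinator's title loosely. That may well be the intention. But Methods gives the same title to the person who faxes the alert, so a reader cannot tell which instruction governs.

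A second objection is that the concern takes the 30-day timing from the sample size and analysis sections and the judgement-laden content from the 90-day definition in Outcomes. This stands in part. A plain 30-day visit, yes or no, leaves a caller less room for judgement. If the 90-day endpoint governs, the blinded day-90 call protects it, although the day-30 report could still feed in. The point is not removed, because Outcomes has the day-30 contact collect both the visit and the uptake of alert recommendations.

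Third, the fact that research study staff complete the form shows only that whoever completes one knows that patient's allocation, not that every staff member does. That is right. A blinded caller may well be available; the text does not identify one.

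Finally, the bias sizes are assumed, and Appendices 6 and 7 are not in the supplied text. Both points are correct. The conclusion does not rest on the simulated rates, and nothing is inferred from the appendices. A neutral script in Appendix 7 would answer the question-wording point but would not settle who makes the call.

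**Conclusion.** The concern holds. The protocol contradicts itself on who makes the day-30 outcome call. Following Outcomes would remove the blinding that Methods plans, for an outcome with no other described check. It should be corrected.

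Confidence in the contradiction is high. Its practical effect is uncertain: it depends on which instruction is followed, on whether the 30-day or 90-day endpoint is primary, and on a reporting bias that the documents do not quantify. On a two-sided test at the planned 49 per arm, 5 to 11 miscounted intervention patients would be enough to produce significance, depending on the starting count (20 or 15) and the continuity correction. The day-90 call is not affected.

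**What to change.** In Outcomes, replace the study coordinator with the allocation-blind staff member described in Methods. State that no one who randomises patients, completes the alert form or faxes it makes outcome calls. Count day 30 from ED discharge, as Methods does.

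If Appendix 7 already holds a neutral script, cite it in Outcomes. If not, use one identically worded script in both arms that does not mention the alert. It should ask whether a primary care visit occurred, its date, whether COPD management was reviewed at that visit, and what changes to COPD treatment or referrals followed.

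To keep the alert-issues part of the endpoint, compare these answers at analysis with each patient's care gaps. Methods says the alert is tailored "to the patients care gap(s) identified during screening", hence before randomisation. Confirm that the gaps are recorded for controls as well; Appendix 6 may already provide for this. This step is secondary to naming the caller.

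The cost is small: a wording change, a named caller who stays out of alert handling, and, only where the appendices do not already cover them, a common script and care-gap recording in both arms. The sample size does not change.

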**Principal analysis of the primary outcome measure:**

The final analysis will be performed on an "intention to treat" basis. Using this approach, patients will be included in the analysis according to the group to which they were randomized. Baseline characteristics in the two treatment arms will be compared using univariate descriptive statistics. The principal analysis of 30-day relapse will be done using an unadjusted  $\chi^2$  comparing the proportion of events in each treatment group. A logistic regression procedure will be employed to adjust raw relapse proportions using significant co-variates (such as patient use of inhaled steroids, current smoking status, etc) which may influence outcomes

We chose the proportion of PCP visits within 30 days as a primary outcome measure rather than survival time to relapse. We believe that it is more relevant to both patients and physicians to know if the enhanced intervention will stimulate a PCP visit rather than examining relapse (which may be affected by age, severity, type of treatment received, smoking status, etc). Therefore, unadjusted  $\chi^2$  followed by logistic regression procedures were chosen over log-rank tests followed by Cox proportional hazards modelling. Both alternative analytic approaches mentioned will still be performed and reported.

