**Principal analysis of the secondary outcome measure:**

All secondary outcome measures will be assessed at 30 days and 90 days and will be analysed using an "intention to treat" analysis. Patients will be contacted to see if they have had an urgent visit (to ED or their PCP). If they describe a relapse (an unscheduled visit for worsening COPD), then we will obtain further information from their medical records and/or treating physician. Those patients who relapse within the first 30 days of the trial will have measurements of oxygenation, airflow obstruction, dyspnea, and quality-of-life done on the day of relapse (either from the family physician or the EDs where they attend). These values will be counted as the last day values for purposes of the analysis (i.e., endpoint analysis, with the last observation carried forward).

Continuous outcome measures including absolute and percent changes in FEV1, oxygen saturation, Transitional Dyspnea Index scores, and changes from Day 1 to Day 30 in the scores of the four components of the Chronic Respiratory Questionnaire will be analysed using either parametric procedures (independent t tests) initially, or with non-parametric methods (Wilcoxon Rank Sum) if the data is not normally distributed. At 90 days, the proportion of patients who achieve

compliance with recommendations (for LAAC, LABA/ICS combinations, and rehabilitation referral), relapse and are hospitalized will be compared using unadjusted  $\chi^2$  tests followed by logistic regression procedures. Survival analyses (log-rank tests followed by Cox proportional hazards modelling) will be used to compare time to relapse.

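### Secondary endpoint 3 (review and adjustment of COPD management) is not the variable tested at day 90 (compliance with three named items), so the listed endpoint has no stated analysis and the tested one is not listed

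*Combined protocol and SAP*

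**What the plan says.** The Outcomes section gives the third secondary endpoint as "review and adjustment of the management of COPD at day 90 post discharge from the ED". It names no items, no denominator, and no rule for a patient who needs no change.

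The section on analysis of the secondary outcomes does not mention review or adjustment. Its management comparison begins "At 90 days, the proportion of patients who achieve" and continues "compliance with recommendations (for LAAC, LABA/ICS combinations, and rehabilitation referral), relapse and are hospitalized will be compared using unadjusted" chi-square tests, followed by logistic regression. It does not say whether compliance means all three items, any one of them, or only those that apply to the patient.

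Two other passages bear on this. Methods says each Alert is individualized "to the patients care gap(s) identified during screening", so patients are expected to differ in what they lack. For the day-30 contact, Outcomes uses a third wording: whether a follow-up visit took place and "if any of the recommendations noted on the Lung Attack Alert have been implemented".

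**The concern.** Endpoint 3 describes something done to the regimen. The analysis section, on its plain reading, describes where the patient stands on three items at day 90. If they are meant to be one endpoint, the plan holds two scoring rules for it. If they are meant to be two, endpoint 3 has no analysis and the compliance test has no listed endpoint. Either way the passages need reconciling.

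This matters because Anticipated Results says the trial will inform whether the Alert improves evidence-based care as well as follow-up, and this endpoint carries much of that claim. A day-90 state also counts patients who complied before randomization. The Alert cannot move them into compliance, so they add equal successes to both arms and weaken the contrast.

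**Working it through.** **Side by side.** Each type of patient scored under each rule, read literally:

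| Patient | Review and adjustment (Outcomes) | Compliance at day 90 (analysis section) |
|---|---|---|
| Already on the recommended items, left unchanged | fails | passes |
| Changed only outside the three items, gap remains | passes | fails |
| Gap in a named item, closed by day 90 | passes | passes |
| Gap in a named item, nothing changed | fails | fails |

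The rules disagree in the first two rows, in opposite directions. The plan itself expects baseline treatment to vary: the primary-analysis section lists covariates "such as patient use of inhaled steroids, current smoking status, etc".

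**Inputs.** The plan gives no rate or power for this endpoint, so there is no figure of its own to reproduce. From the documents: 49 patients per group and alpha 0.05 (Sample Size Considerations). Assumed, not in the documents:
- a share b of each arm is already compliant at baseline and stays so;
- among the rest, the gap is closed in 20% of controls and 50% of Alert patients;
- closing the gap makes the patient compliant, so any-gap and all-gaps rules coincide;
- there are no changes outside the three items.

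The test is a two-sided uncorrected chi-square, with power by exact enumeration. The sample-size section says "we used 1-tailed estimates due to the assumption that the intervention will not" decrease follow-up, but that concerns PCP visits. The plan does not state a one-sided test for this endpoint.

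**Formulas.**
- Day-90 compliance, all patients: b + (1 − b) × 0.20 v b + (1 − b) × 0.50
- Gap closure, all patients (what the adjustment rule reduces to here): (1 − b) × 0.20 v (1 − b) × 0.50
- Gap closure, patients with a gap: 0.20 v 0.50, with about 49 × (1 − b) per arm

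**Results.**

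| b | Compliance, all | Power | Gap closure, all | Power | With a gap, per arm | Power |
|---|---|---|---|---|---|---|
| 0.2 | 36% v 60% | 0.68 | 16% v 40% | 0.77 | 39 | 0.81 |
| 0.4 | 52% v 70% | 0.45 | 12% v 30% | 0.61 | 29 | 0.67 |
| 0.6 | 68% v 80% | 0.27 | 8% v 20% | 0.43 | 20 | 0.53 |

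At b = 0 all three coincide (20% v 50%, power 0.89).

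The two all-patient rules have the same absolute difference, 0.30 × (1 − b): at b = 0.4, 70 − 52 = 18 points and 30 − 12 = 18 points. Their odds ratios differ: (0.30/0.70)/(0.12/0.88) = 3.1 for gap closure and (0.70/0.30)/(0.52/0.48) = 2.2 for compliance.

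**Changes outside the three items.** These raise only the adjustment rate. At b = 0.4, suppose a further 10% of each arm have such a change and no gap closure. Adjustment becomes 22% v 40%, power 0.49, against an unchanged 0.45 for compliance. The control-arm gap between the rules falls from 52 − 12 = 40 points to 52 − 22 = 30. At b = 0.2 with a further 20%, both rules give 36% v 60% and power 0.68.

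**The case against.** The strongest reply is that the analysis section simply makes endpoint 3 operational. Achieving compliance can mean moving into it, rehabilitation referral is an event rather than a state, and the recommendations are specific to each patient's gaps. On that reading the already-compliant patient is no longer a success at day 90, and the dilution goes with that case. This is a fair reading and the text does not exclude it. But the text does not say it either, and a change outside the three items would still count in one section and not in the other.

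The operational definition may also sit in Appendix 6 (data collected) or Appendix 7 (follow-up questions), which were not supplied. If so, the two sections still need to be brought into line with it.

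A reader might infer more than the documents support:
- *That the analyst can choose between two results after seeing both.* Only one between-arm management test is planned at day 90. The defect is a mismatch of labels and scoring, not two competing tests.
- *That this is the only endpoint showing changed care.* The primary endpoint's wording includes dealing with issues on the Alert, and the day-30 contact asks about implemented recommendations.
- *That patients changed outside the three items drive the two rules' results further apart.* More patients are then classified differently, but with equal shares in both arms the rates and power move closer, as shown in the working.

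**Conclusion.** The point stands as a defect of definition in one secondary endpoint. Endpoint 3 has no stated analysis, the compliance variable is not among the listed endpoints, and on the literal reading the two score some patients in opposite ways. If compliance is read as a day-90 state, patients compliant before randomization dilute the between-arm comparison.

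The size is unknown. Under the assumed closure rates, with 20% to 60% already compliant, power runs from 0.68 down to 0.27 for day-90 compliance and from about 0.81 down to 0.53 for gap closure among patients with a gap. These figures illustrate the mechanism and do not estimate what the trial would see. A reader might infer from them that the conclusion of the trial is at risk. It is not: the primary endpoint and the sample size do not depend on this variable.

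**What to change.** Use one definition in both the Outcomes and the secondary-analysis sections:
- **Endpoint:** closure by day 90 of a guideline gap in the three items the analysis section already names, recorded before randomization in both arms.
- **Denominator:** patients with at least one such gap, analysed as randomized. Because the gap is fixed before allocation, the comparison remains a randomized one.
- **Rule:** state whether any gap or all gaps must be closed.
- **Scoring:** the same in both arms, from the day-90 contact by staff unaware of allocation that Methods already plans.

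Report descriptively day-90 compliance in all randomized patients, reviews that led to no change, and changes outside the three items.

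The cost is mostly wording, with one practical demand. Methods says gaps are identified at screening but describes the Alert form being completed only for the intervention group, so the pre-randomization gap list must also be kept for controls. This includes patients randomized by phone the morning after discharge. Patients without a gap leave this one secondary test, and changes outside the three items are reported but not tested.
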